5.8.3. Vital Signs

Vital signs parameters include weight (kg), heart rate, systolic and diastolic blood pressure, respiratory rate, and temperature (°C). For each parameter at each time point, the change from baseline to post baseline will be summarized.

Plots of vital sign parameters for both mean observed and mean change from baseline will be presented for each parameter. Vital signs will also be listed for all patients.

5.8.4. Echocardiogram (ECG) Results

The quantitative ECG assessments (ventricular rate, QRS width, PR interval, and QTc interval) will be summarized at each time point.

ECG overall interpretation (normal, abnormal not clinically significant and abnormal clinically significant) will be presented for actual values and changes from baseline (Screening observation) to each post baseline visit [expressed as Improvement, No Change, and Deterioration].

Note:

- Improvement = Abnormal Clinically Significant (CS) to Abnormal Not Clinically Significant (NCS)/Normal, Abnormal NCS to Normal
- Deterioration = Normal to Abnormal NCS/CS, Abnormal NCS to Abnormal CS
- No change = Normal to Normal, Abnormal NCS to Abnormal NCS, Abnormal CS to Abnormal CS

If either result is missing for any patient, then an 'Unknown' category will be presented.

ECG results will be listed for all patients.

5.8.5. Physical Examination

Physical exam details will be listed only.

5.8.6. Post-treatment Follow-up and Long-term Follow-up

A listing of post-treatment follow-up and Long-term follow-up data including the visit date, malignancy status, and survival status will be provided.

5.9. Pharmacokinetics Analysis

5.9.1. Pharmacokinetic Sampling Schedule

Blood samples will be collected from all patients at the following schedule:

Visit	Study Day
Cycle 1 Day 1	1
Cycle 1 Day 8	8
Cycle 2 Day 1	22
Cycle 9 Day 1	169
Cycle 9 Day 8	176
Cycle 10 Day 1	190
Cycle 17 Day 1	337
Cycle 17 Day 8	344

5.9.2. Data Handling

Concentrations that are below the limit of quantitation (BLQ) prior to the first dose will be assigned a numerical value of zero. Post-treatment concentrations that are BLQ will be treated as missing.

Concentrations assigned a value of missing will be omitted from the descriptive statistics. A concentration value of zero will be excluded from the computation of the geometric mean (geometric CV%). If any patients are found to be noncompliant with respect to dosing, have incomplete data, or encounter other circumstances that would affect the evaluation of pharmacokinetics, a decision will be made on a case-by-case basis as to their inclusion in the pharmacokinetic analysis. Data excluded from pharmacokinetic analysis will be included in the data listings, but not in the summaries.

In tables and listings for the derived pharmacokinetic data, there should be four decimal places for numerical values below 1, three decimal places for numeric values below 10 but above 1, and two decimal places for numeric values above 10. However, the listings of raw data should not have more decimal places than the actual data.

5.9.3. Pharmacokinetic Analysis

All ACE-536 serum concentrations will be listed by patient and scheduled time (visit and study). Actual dosing/sampling time, sample time relative to first dosing time, visit, and concentration as done for the 04 study will be presented in the listing.

The ACE-536 serum concentrations will be summarized by scheduled time, including N (number of observations), arithmetic mean, arithmetic standard deviation (SD), arithmetic coefficient of variation (CV%), geometric mean, geometric CV%, minimum, median, and maximum. Mean (SD) serum concentration-time profiles will be presented on linear scales.

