- 12 **Serum folate:** Required at screening for patients with treatment interruption to confirm eligibility. Required for all patients at C1D1, C5D1, C13D1, C21D1, C29D1 C37D1, C45D1, C53D1, C61D1, C69D1, C77D1, and EOT.
- 13 **Hematology:** RBC, nucleated red blood cells (nRBC) (local and central lab), white blood cell (WBC) with differential, hemoglobin, hematocrit, reticulocyte count, platelet count, mean corpuscular volume (MCV), mean corpuscular hemoglobin (MCH), mean corpuscular hemoglobin concentration (MCHC), and red blood cell distribution width (RDW). On dosing days, hemoglobin values are to be drawn and resulted (up to 24 hours) prior to dosing (see [Section 10.8](#), Patient Dose Modification Rules).
- 14 **Peripheral blood smear:** Peripheral blood smears will be prepared centrally from blood sample.

15 **Chemistry:** Sodium, potassium, AST, ALT, LDH, total bilirubin, indirect bilirubin, alkaline phosphatase, blood urea nitrogen (BUN)/urea, creatinine, GGT, calcium, phosphorus, glucose, amylase, lipase, total protein, albumin, and uric acid. Perform at screening, C1D1, C3D1, C5D1, C9D1, C13D1, C17D1, C21D1, C25D1, C29D1, C33D1, C37D1, C41D1, C45D1, C49D1, C53D1, C57D1, C61D1, C65D1, C69D1, C73D1, C77D1, C81D1, EOT and EOS.

16 **Urinalysis by dipstick analysis (local lab):** pH, specific gravity, protein, glucose, ketones, blood, leukocyte esterase, and nitrite, with microscopic examination if indicated. **Urine chemistry (central lab):** urine chemistries include but are not limited to: microalbumin and creatinine.

17 If the patient has a **positive ADA** result at their last assessment, the patient may be asked to return approximately every three months for additional testing, until a negative result is obtained or the result is considered stabilized.

18 **PK collection** is only required on C1D1, C1D8, C2D1, C9D1, C9D8, C10D1, C17D1, and C17D8.

19 **PD biomarkers:** May include hepcidin, GDF15, GDF8, GDF11, activin A and others to be determined. The sponsor may perform additional sample analysis for biomarkers for exploratory research purposes only.

20 **Hemoglobin electrophoresis:** Samples will be collected for central hemoglobin electrophoresis on C1D1, C5D1, C13D1, C21D1, C29D1, C37D1, C45D1, C53D1, C61D1, C69D1, C77D1, EOT, and EOS.

21 **Pregnancy test:** (urine or serum) is required for female patients of child bearing potential only.

22 **Menstrual history:** is required for female patients of child bearing potential only

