7.3. Summary of Clinical Experience

The safety, tolerability, pharmacokinetics (PK), and pharmacodynamics (PD) effects of ACE-536 was evaluated in healthy postmenopausal women in a phase 1, randomized, double-blind, placebo controlled, multiple ascending dose study (Study A536-02). The primary objective of the study is to evaluate the safety and tolerability of ACE-536 in this population. Secondary objectives of the study are to examine the PK parameters and PD effects of ACE-536.

A total of 32 subjects were enrolled. Eligible subjects were healthy, postmenopausal women, 45-75 years old. The anticipated PD effect was an increase in plasma hemoglobin level. Screening and baseline hemoglobin values had to be between 11.0 and 14.5 g/dL, inclusive, to mitigate the risk of substantial excursions above the normal range. Sequential cohorts of 8 subjects each were randomized to receive either ACE-536 (n=6) or placebo (n=2) administered as a SC injection on Day 1 and Day 15. Each subject was to be followed for 112 days (16 weeks) after receiving their last dose of ACE-536 or placebo. The following dose levels were evaluated: 0.0625, 0.125, and 0.25 mg/kg.

ACE-536 administered every 2 weeks by subcutaneous (SC) injection for one or two doses at dose levels of 0.0625, 0.125 or 0.25 mg/kg was generally safe and well-tolerated in healthy postmenopausal female subjects. No serious or severe adverse events (AE) were reported. The majority of AEs were considered mild in severity. AEs that were considered at least possibly drug-related across ACE-536 dose groups included injection site hemorrhage (3 subjects), injection site macule (2 subjects), and dry skin, macule, hyperesthesia, muscle spasms, myalgia, generalized pruritus, and papular rash (1 subject each). Injection site pain was reported in one placebo-treated subject.

PK results indicated mean AUC and C_{max} values increased in a dose-proportional manner with ACE-536 dose level; mean T_{max} ranged from 7.0 to 9.8 days, and mean $T_{1/2}$ ranged from 14.9 to 16.2 days after the first dose. These PK results support intermittent SC dosing of ACE-536 in future studies, e.g., every 3 weeks.

PD assessments for hematological markers showed increases in hemoglobin levels at the 0.125 mg/kg dose level and more consistently at the 0.25 mg/kg dose level. Small increases in

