10. TREATMENT OF PATIENTS

10.1. Selection and Timing of Dose for Each Patient

Once a patient is enrolled, the appropriate dose of ACE-536 will be administered as an SC injection on Cycle 1 Day 1. Subsequent doses will be administered every 3 weeks on Day 1 of the cycle for up to 87 cycles. Patients may not exceed 87 cycles or 1825 days after first dose, whichever occurs first. The last dose of ACE-536 may not be administered after Day 1825, regardless of the number of cycles completed. Dose reductions may be required for individual patients as outlined in the Patient Dose Modifications Rules ([Section 10.8](#)). If a dose delay is required, the patient will return weekly for assessment of hematology results and AEs until the patient is eligible to receive the next dose of ACE-536. Patients will be asked to return to the clinic for two follow-up visits, occurring approximately 28 days and 56 days after their last dose of ACE-536. Dose level titration increases may also occur for individual patients as outlined in the Individual Dose Titration rules ([Section 10.9](#)). If a patient has a positive ADA result at the last visit, the patient may be asked to return for additional ADA testing every three months, until a negative result is obtained or the result is considered to be stabilized.

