12.2. Dosing Days and Interim Visits

- Study procedures must be done prior to administration of study drug. All patients must be assessed for eligibility prior to dosing on C1D1. C1D1 MRI for LIC

(at selected sites) and EMH masses (unless site does not have feasibility to perform the assessment) and MRI of the spleen (if no prior splenectomy) can be performed up to 56 days prior to C1D1. If performed as part of standard of care, MRI for LIC, MRI for EMH and spleen do not need to be repeated. All screening and Cycle 1 Day 1 procedure results required to confirm eligibility must be obtained and reviewed prior to study drug administration in A536-06.

- On dosing days: Note that the patient dose must be calculated based on the patient's weight on the day of dosing. Starting dose level for C1D1, dose modification rules and titration rules must be reviewed and implemented prior to dosing as required per protocol (see [Sections 10.7, 10.8, 10.9](#)). If a dose delay is required per the dose modification rules (Section 10.8), the patient will not be dosed. The patient will return weekly for assessment of hematology results and AEs until the patient is eligible to receive the next dose of ACE-536 and start the next cycle. The patient should resume the study at the planned dosing cycle (e.g. if the patient missed a dose at C4D1, then they would resume dosing at C4D1 and not skip to C5D1).
- The hematology results can be collected up to 24 hours prior to the dosing day. For patients with treatment interruption, the hemoglobin should be available to confirm eligibility within one day prior to C1D1.
- Patients should be monitored for AEs throughout the study. All AEs and abnormal findings that might require modification of dosing (see [Section 10.8](#)) should be reviewed prior to dosing to ensure that the patient is still eligible to receive additional doses of ACE-536.
- Pregnancy test (urine or serum) and menstrual history is required of female patients of child bearing potential only.
- Physical exam should include an optional evaluation of gonadal size in male patients at timepoints specified in the Schedule of Events ([Section 2](#)).
- If at any visit the systolic blood pressure is ≥ 150 mmHg, the diastolic blood pressure is ≥ 95 mmHg and/or the absolute increase in either measure from baseline is ≥ 20 mmHg, perform one repeat of the blood pressure assessment after a minimum of 15 minutes.

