15.2.4. Pharmacokinetics Analysis

PK parameters for ACE-536, such as maximum serum concentration (C_{max}), time to maximum concentration (t_{max}), and area under the concentration/time curve (AUC), will be estimated using non-compartmental and/or single compartment analysis, as appropriate. Dose proportionality may be assessed using the exposure data (e.g., C_{max} , AUC) if sufficient dose levels are studied. Descriptive statistics will be provided for serum concentrations and PK parameters. The relationship between ACE-536 exposure and response (i.e., safety, efficacy, and biomarkers) may be explored, as appropriate.

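### PK concentrations are summarised by nominal visit without regard to time since the preceding dose, and the SAP drops the protocol's PK parameters without recording it

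*SAP*

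**What the plan says.** **Summary basis.** SAP 5.9.3: "The ACE-536 serum concentrations will be summarized by scheduled time". SAP 5.9.1 fixes those times as study days, for example C9D1 as Day 169 and C10D1 as Day 190. On the listing, 5.9.3 says: "Actual dosing/sampling time, sample time relative to first dosing time, visit, and concentration as done for the 04 study will be presented in the listing".

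**Dosing and delays.** Protocol 10.1: "Subsequent doses will be administered every 3 weeks on Day 1 of the cycle for up to 87 cycles". Visit windows run from the previous dose (Schedule of Events, note 2). Under Protocol 10.8 a held dose is reviewed weekly until the condition for resuming is met, with no stated maximum. The visit name does not move. Protocol 12.2 gives the example: "if the patient missed a dose at C4D1, then they would resume dosing at C4D1 and not skip to C5D1".

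**Sampling.** Schedule of Events, note 18: PK collection "is only required on C1D1, C1D8, C2D1, C9D1, C9D8, C10D1, C17D1, and C17D8". Procedures precede dosing, so the five Day 1 samples are pre-dose and the three Day 8 samples are post-dose. There is no sample at C18D1.

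**Parameters.** Protocol 15.2.4 names Cmax, tmax and AUC as examples of parameters that "will be estimated using non-compartmental and/or single compartment analysis, as appropriate". SAP 5.9.3 contains concentration listings, summaries and profiles only. SAP 5.9.2 sets decimal places for derived PK data that the SAP nowhere defines. The table of changes in SAP 5.12.6 covers baseline hemoglobin and the removal of the EE population, and nothing on PK.

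**The concern.** A pre-dose concentration can be interpreted only against the time since the last dose. Where that time varies under one visit label, the mean and CV% for the visit partly describe dosing delays. The delays are not random: Protocol 10.8 triggers holds for high hemoglobin and for related adverse events, so the distortion falls on patients who matter to any exposure-response reading. C1D1 has a second problem: it pools patients still carrying A536-04 drug with patients close to washout.

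Separately, the PK profile is a stated secondary objective, and the protocol's parameters disappear between protocol and SAP. Protocol 15.5 requires departures from the protocol's analyses to be indicated in the SAP.

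**Working it through.** **1. Nominal days.** Study day = 1 + 21 × (cycle − 1) + (day − 1). C9D1: 1 + 168 = 169. C10D1: 1 + 189 = 190. C17D8: 1 + 336 + 7 = 344. All eight days in SAP 5.9.1 reproduce, but only when no dose is ever late.

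**2. Days since the preceding dose at a pre-dose visit.** Gap = 21 ± window + 7 × number of weekly holds. The schedule prints ±5 days for C2D1. For Cycles 6-17 the column label prints ±2 days, although those cycles repeat Cycles 2-5, whose Day 1 windows are ±5.

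| Weekly holds (assumed) | Gap with ±5 d | Gap with ±2 d |
|---|---|---|
| 0 | 16-26 | 19-23 |
| 1 | 23-33 | 26-30 |
| 2 | 30-40 | 33-37 |
| 3 | 37-47 | 40-44 |

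This affects C2D1, C9D1, C10D1 and C17D1. Day 8 samples are timed from their own cycle's dose (±2 days).

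**3. Effect on the trough.** Inputs from Protocol 7.3 (healthy volunteers): half-life 14.9-16.2 days, Tmax 7.0-9.8 days. One-compartment model with first-order absorption: ke = ln 2 / half-life; ka solves ln(ka/ke)/(ka − ke) = Tmax, giving 0.19-0.34 per day. Concentrations are summed over eight doses every 21 days, and the gap after the eighth is varied. Relative to a 21-day trough:

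| Gap (days) | Ratio |
|---|---|
| 16 | 1.21-1.25 |
| 19 | 1.08-1.10 |
| 23 | 0.91-0.92 |
| 26 | 0.79-0.82 |
| 28 (one-week hold) | 0.72-0.75 |
| 35 (two-week hold) | 0.52-0.56 |
| 42 (three-week hold) | 0.38-0.42 |

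A check from half-life alone: 2^(−7/14.9) = 0.72 and 2^(−21/14.9) = 0.38. With no hold at all, Day 16 against Day 26 is a 1.47- to 1.58-fold difference.

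**4. The C1D1 row.** Roll-over patients are 28 ± 7 = 21 to 35 days after their last A536-04 dose (Protocol 9.1). Interrupted patients are at least 28 days past an A536-04 EOS visit that is nominally 56 days after the last dose (SAP Appendix 3, note 13): 56 + 28 = 84 days, or 21 + 21 + 28 = 70 if both the EOT and EOS visits fell a week early. After five A536-04 doses the model ratio of Day 28 to Day 84 is 10.9-13.5; half-life alone gives 2^(56/16.2) = 11.0 to 2^(56/14.9) = 13.5.

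**5. What AUC is recoverable.** Cycle 1 (C1D1, C1D8, C2D1) and Cycle 9 (C9D1, C9D8, C10D1) each have samples at nominal days 0, 7 and 21 of the interval. The linear trapezoid is 7 × (C0 + C7)/2 + 14 × (C7 + C21)/2. Against the model's true AUC(0-21 d) it returns 0.88-0.89 in Cycle 1 without carry-over, 0.93-0.95 in Cycle 1 for a roll-over patient 28 days after the fifth A536-04 dose, and 0.95-0.96 in Cycle 9. If a closing sample taken at day 42 is treated as day 21, the Cycle 1 figure without carry-over falls to 0.70-0.73. Cycle 17 has no closing sample, so it has no full-interval non-compartmental AUC.

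**The case against.** A reader might infer that samples are timed only from the first dose and that AUC cannot be obtained. The documents do not support that. The listing also carries actual dosing and sampling times, so time since the preceding dose can be worked out, and AUC for Cycles 1 and 9 can be derived with a modest shortfall. AUC is unspecified, not underivable.

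A reader might also take six weeks or more between dose and trough as a feature of the plan. It is not a document figure: 42 days assumes three weekly holds, no hold frequency is given, and the longest gap without a hold is 26 days, or 23 under the ±2 day label.

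The SAP has some safeguards. Section 5.9.2 lets irregular cases be left out of the PK summaries, so pooling of long-hold samples is possible but not certain. That provision is decided case by case and sets no criterion. Section 5.12.1 promises data-driven analysis windows in programming specifications, but does not mention time since dose.

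The protocol's wording on parameters is qualified: the three are examples, estimated as appropriate, and dose proportionality and exposure-response are optional. Nor is exposure unmeasured, since Day 8 and pre-dose concentrations are tabulated. An observed tmax from a single within-interval sample is uninformative, but the protocol also allows a one-compartment fit. These points lower the severity; they do not supply a rule for delayed samples or explain the missing parameters.

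Finally, dose level (0.2 to 1.25 mg/kg, a 6.25-fold range) is not separated in these summaries and may add more spread than one hold.

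**Conclusion.** The concern holds in limited form. The SAP's stated summary rule can pool pre-dose samples that are not comparable, and it does so structurally at C1D1 whenever both roll-over and interrupted patients contribute. The size is about 1.5-fold from a ±5 day window alone (about 1.2-fold under ±2), 0.72-0.75 of the 21-day trough after a one-week hold, 0.38-0.42 after three, and about 11- to 13.5-fold between Day 28 and Day 84 at C1D1. Omitting the protocol's PK parameters without an entry in 5.12.6 is a separate documentation gap and does not depend on any model.

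The ratios assume that half-life and Tmax from healthy postmenopausal women at 0.0625-0.25 mg/kg apply to these patients at higher doses, and that kinetics are linear and one-compartment. How many samples are affected cannot be known from the documents. PK is a descriptive secondary objective with no hypothesis test, so severity is low to moderate.

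**What to change.** In SAP 5.9.3:

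1. Add to the listing the time since the preceding dose, and that dose, derived from the actual times already recorded.
2. Summarise pre-dose and Day 8 samples by visit only when they fall within a pre-stated window of the preceding dose. First reconcile the ±2 and ±5 day labels for Cycles 6-17. Summarise out-of-window samples separately rather than dropping them, because delayed patients are a selected group. Show C1D1 separately for roll-over and interrupted patients.
3. Either report AUC(0-21 d) from actual times for Cycles 1 and 9 (or a one-compartment fit), stating that Cycle 17 has no closing sample and that an observed tmax is not informative; or record in 5.12.6 that the protocol's PK parameters are not derived, with the reason.

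The cost is SAP wording and reprogramming from existing data, with no new samples and no change to dosing. The price is fewer values in each visit row and a stated limit on Cmax and tmax. Some spread remains inside any window, which the listed times and doses let a reader judge.

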10.7. Starting Dose Levels

A patient without treatment interruption may continue to be dosed with ACE-536 at the same dose level (rounded to nearest A536-06 starting dose level) administered at their last dose in study A536-04 (unless a dose reduction is required based upon patient dose modification rules from study A536-06). All patients with treatment interruption will be initially treated with ACE-536 at a starting dose level of 0.8 mg/kg which has been determined to be safe and well tolerated by the Safety Review Team (SRT) based on data from study A536-04. Examples of possible starting dose levels with dose modifications (reductions and titrations) are below for reference.

Table 2: Examples of Possible Starting Dose with Dose Modifications (Reductions and Titrations)

3 rd Dose Reduction	2 nd Dose Reduction	1 st Dose Reduction	Starting Dose Level	1 st Dose Titration	2 nd Dose Titration
	0.2 mg/kg	0.4 mg/kg	0.6 mg/kg	0.8 mg/kg	1.0 mg/kg
0.2 mg/kg	0.4 mg/kg	0.6 mg/kg	0.8 mg/kg	1.0 mg/kg	1.25 mg/kg
0.4 mg/kg	0.6 mg/kg	0.8 mg/kg	1.0 mg/kg	1.25 mg/kg	
0.6 mg/kg	0.8 mg/kg	1.0 mg/kg	1.25 mg/kg		

- Starting dose level for TD and NTD patients to be determined based on data from study A536-04 (range: 0.2-1.25 mg/kg).
- Starting dose level for patients without treatment interruption will be last dose level (rounded to nearest A536-06 starting dose level) administered in study A536-04 (unless a dose reduction is required based upon patient dose modification rules from study A536-06).
- Patients may be titrated up and down dose levels as required per protocol to meet dose modification and titration rules.
- Patients who require more than 2 dose reductions due to an AE should be discontinued from treatment and complete the EOT and EOS visits.
- The maximum dose titration will not exceed the maximum dose level tested in base study A536-04.

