3.1. Study Design

Consenting patients that meet the A536-06 eligibility criteria may immediately roll over from A536-04 to study A536-06 following the last ACE-536 dose. These patients may forego the End of Study (EOS) visit in study A536-04 to begin study A536-06. For these patients, Cycle 1 Day 1 (C1D1) of study A536-06 may take place 28 (\pm 7) days after the last dose administered in study A536-04, which may coincide with the patient's A536-04 End of Treatment (EOT) visit. These patients are considered "patients without treatment interruption".

Patients who complete the EOS visit for study A536-04 and are \geq 28 days post EOS visit are considered "patients with treatment interruption" and will be re-assessed for eligibility by meeting all eligibility criteria plus additional inclusion criteria, as defined in Section 9.3 of the protocol.

Patients who do not meet the above criteria (e.g., $>$ 35 days after last dose in study A536-04 and $<$ 28 days post EOS visit in study A536-04) may still participate, but should be treated as patients with treatment interruption and should not begin study A536-06 C1D1 until they have reached \geq 28 days post EOS visit from study A536-04 so that new baseline assessments can be measured.

For patients without treatment interruption, transfusion status (NTD or TD) will carry-over from the base study A536-04. For NTD patients with treatment interruption, transfusion status will be reassessed prior to C1D1 of study A536-06. NTD patients with treatment interruption are defined as patients who require transfusion of $<$ 4 units of RBCs over the 8 weeks prior to Cycle

1 Day 1 of study A536-06. For TD patients with treatment interruption, transfusion status will carry-over from the base study A536-04.

A patient without treatment interruption may continue to be dosed with ACE-536 at the same dose level (rounded to nearest A536-06 starting dose level) administered at their last dose in study A536-04 (unless a dose reduction is required based upon patient dose modification rules from study A536-06). All patients with treatment interruption will be initially treated with ACE-536 at a starting dose level of 0.8 mg/kg which has been determined to be safe and well tolerated by the Safety Review Team (SRT) based on data from study A536-04. Examples of possible starting dose levels with dose modifications (reductions and titrations) are below for reference.

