Table 1: Examples of Possible Starting Dose with Dose Modifications (Reductions and Titrations)

3 rd Dose Reduction	2 nd Dose Reduction	1 st Dose Reduction	Starting Dose Level	1 st Dose Titration	2 nd Dose Titration
0.2 mg/kg	0.4 mg/kg	0.6 mg/kg	0.8 mg/kg	1.0 mg/kg	1.25 mg/kg
0.4 mg/kg	0.6 mg/kg	0.8 mg/kg	1.0 mg/kg	1.25 mg/kg	
0.6 mg/kg	0.8 mg/kg	1.0 mg/kg	1.25 mg/kg		

- Starting dose level for TD and NTD patients to be determined based on data from study A536-04 (range: 0.2-1.25 mg/kg).
- Starting dose level for patients without treatment interruption will be last dose level (rounded to nearest A536-06 starting dose level) administered in study A536-04 unless a dose reduction is required based upon patient dose modification rules from study A536-06.
- Patients may be titrated up and down dose levels as required per protocol to meet dose modification and titration rules.
- Patients who require more than 2 dose reductions due to an AE should be discontinued from treatment and complete the EOT and EOS visits.
- The maximum dose titration will not exceed the maximum dose level tested in base study A536-04.
- Each TD patient will have a defined “pre-transfusion hemoglobin threshold” which will be calculated based on transfusion history and will be used for determining when to transfuse during the study. The baseline pre-transfusion hemoglobin threshold will be the mean of all documented pre-transfusion hemoglobin values during the 12 weeks prior to C1D1 of base study A536-04 (for patients without treatment interruption) or study A536-06 (for patients with treatment interruption). During treatment, if the pre-transfusion hemoglobin level is increased by ≥ 1 g/dL compared to the baseline pre-transfusion hemoglobin threshold for that patient, transfusion should be delayed by a minimum of 7 days and/or the number of units transfused should be reduced by 1 or more RBC units. Patients may be transfused at the investigator’s discretion for symptoms related to anemia or other requirements (e.g., infection).

Patients will participate in the extension study A536-06 for up to 97 months, including a 28-day (1 month) screening period, a 60-month treatment period and a 3-year (36 months) follow-up period.

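### The planned PK table groups concentrations by visit only, so its means and CVs confound dose with pharmacokinetic variability

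*SAP*

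**What the plan says.** SAP 5.9.3 defines the whole PK output. The summary reads "The ACE-536 serum concentrations will be summarized by scheduled time, including N (number of observations", followed by arithmetic and geometric means and CVs, minimum, median and maximum. For the plots, "Mean (SD) serum concentration-time profiles will be presented on linear scales". The listing is to show "Actual dosing/sampling time, sample time relative to first dosing time, visit, and concentration as done for the 04 study"; dose is not among the items named. The only general split that the SAP mentions (5.2) is TD versus NTD.

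Dose is not constant. SAP 3.1 says "All patients with treatment interruption will be initially treated with ACE-536 at a starting dose level of 0.8 mg/kg", while patients without interruption continue at their last A536-04 level. Protocol 10.7 gives the permitted starting levels as "range: 0.2-1.25 mg/kg". Protocol 10.9.1 and 10.9.2 assess titration on Day 1 of every cycle from C3D1. SAP 5.9.1 samples at C1D1, C1D8, C2D1, C9D1, C9D8, C10D1, C17D1 and C17D8.

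The PK profile is a secondary objective (Protocol 8.2). Protocol 15.2.4 adds that "Dose proportionality may be assessed using the exposure data", but SAP 5.9 does not take this up.

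**The concern.** Concentration depends on dose as well as on the patient's clearance. A table grouped by visit alone mixes the two. Its mean describes no particular dose, and its CV combines the spread in dose with the spread between patients on the same dose.

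The comparison over time is also affected. The samples at Cycles 9, 10 and 17 come after several titration opportunities, and those at Cycle 1 come before any. A higher mean later on could be accumulation, a change in clearance, or simply higher doses.

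Cycle 1 has a further problem. Rollovers arrive with drug still in the circulation, and interrupted patients arrive with little. One C1D1 mean covers both states, and carry-over also affects C1D8 and C2D1.

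**Working it through.** The plan states no CV or expected concentration, so there is no figure of its own to reproduce.

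**1. Spread from dose alone.** Assume concentration = dose × patient factor, with the two independent. The levels come from Protocol 10.7, Table 2. The mixes are assumptions, because the documents do not say how many patients are on each level. CV_dose = SD of dose / mean dose.
- 0.8, 1.0 and 1.25 equally: mean 1.017, SD 0.184, CV 18%.
- 0.6, 0.8, 1.0 and 1.25 equally: mean 0.912, SD 0.241, CV 26%.
- All six levels equally: mean 0.708, SD 0.354, CV 50%.

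**2. Effect on the reported CV.** Let CV_b be the same-dose between-patient CV, which is also not given. Then CV_total² = (1 + CV_dose²)(1 + CV_b²) − 1, and the dose share is CV_dose² / (CV_dose² + CV_b²).

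| Assumed mix (mg/kg) | CV_dose | CV_total if CV_b = 40% | Dose share at CV_b 30 / 40 / 50% |
|---|---|---|---|
| One dose | 0% | 40% | 0 / 0 / 0% |
| 10/20/70% at 0.8/1.0/1.25 | 13% | 42.5% | 17 / 10 / 7% |
| Equal 0.8/1.0/1.25 | 18% | 44.5% | 27 / 17 / 12% |
| Equal 0.6 to 1.25 | 26% | 49% | 44 / 30 / 22% |
| Half at 0.8, rest spread evenly | 37% | 57% | 61 / 47 / 36% |
| Equal, all six levels | 50% | 67% | 74 / 61 / 50% |

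For example, all six levels at CV_b 40%: √(1.25 × 1.16 − 1) = √0.45 = 67%. Summarised by dose or dose-normalised, each row returns to 40%.

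**3. Change over time.** A patient starting at 0.8 mg/kg can step up at C3D1 and, after two cycles at the new level, again at C5D1. That reaches 1.25 before the Cycle 9 sample. Under proportionality, concentration rises by 1.25/0.8 = 1.56 with unchanged PK. A TD patient who stays at 4 units per 8 weeks receives 3 units per 6 weeks, which meets the trigger in Protocol 10.9.2. Compare this with the accumulation expected from dosing every 21 days, using the half-lives of 14.9 to 16.2 days in Protocol 7.3 and a one-compartment approximation: 1/(1 − 2^(−21/14.9)) = 1.60, and 1.69 for 16.2 days. Titration and accumulation can thus produce changes of similar size, and a by-visit mean cannot separate them.

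**4. Cycle 1 by entry route.** Rollovers are sampled a nominal 28 (±7) days after their last dose (SAP 3.1). Interrupted patients are at least 28 days past an EOS visit that falls 56 days after the last dose (SAP Appendix 3), so nominally 84 days or more. Protocol 7.3 gives a mean Tmax of 7.0 to 9.8 days, so decay is counted from the peak.
- Rollovers: 2^(−(28 − 7.0)/14.9) = 38% to 2^(−(28 − 9.8)/16.2) = 46% of the peak.
- Interrupted: 2^(−(84 − 7.0)/14.9) = 3% to 2^(−(84 − 9.8)/16.2) = 4% of the peak.

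The two groups differ about 11- to 14-fold relative to their own last peak.

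**The case against.** Pooling is inferred from silence: the SAP does not say that dose will be ignored, and a programmer could add it. Concentrations are listed by patient and SAP 5.5 lists administration details, so dose can be linked afterwards. This is true, but a plan followed as written produces only the by-visit table.

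A reader might infer that the means and CVs would mainly reflect the dose mix. The documents do not support that. The 0.2 to 1.25 mg/kg span is the permitted starting range, not an observed distribution. The example tables show starting levels of 0.6 to 1.25, with 0.2 and 0.4 appearing only as reductions. For the mixes tried within 0.8 to 1.25 mg/kg, between-patient variability exceeds the dose contribution at every same-dose CV tried, from 20% to 60%.

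A reader might also take proportionality as established. Protocol 7.3 does report that AUC and Cmax "values increased in a dose-proportional manner with ACE-536 dose level", but in healthy postmenopausal women given one or two doses of 0.0625 to 0.25 mg/kg. Extending it to this trial is an assumption.

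Nor does it follow that an anti-drug antibody effect on PK could never be examined. Protocol 15.2.5 plans that exploration separately, and SAP 5.12.6 does not list it as dropped.

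Finally, dose normalisation has limits. With 38% to 41% of a dose's contribution left after 21 days (2^(−21/14.9) and 2^(−21/16.2)), dividing by the last dose alone is biased just after a titration. At C1D1 it is uninformative for interrupted patients. The fix has to allow for both.

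**Conclusion.** The point holds in a limited form. As specified, the by-visit summary confounds dose with PK variability for any mix other than a single dose, and a shift from Cycle 1 to Cycle 9 or 17 cannot be attributed to accumulation or time-dependence. The amount is unknown. Dose alone adds a CV of 0% to 50% across the assumed mixes, and the dose share of variability runs from 0% to about 75% for same-dose CVs of 30% to 50%. These figures assume approximate proportionality and independence of dose from the patient factor. Titration follows response, so independence may not hold exactly. The Cycle 1 contrast rests on nominal visit timing and on half-lives and Tmax from healthy volunteers.

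This is a cheap improvement. The analysis is descriptive and secondary, and no sample size, error rate or primary safety conclusion depends on it.

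**What to change.** Keep the by-visit table and add the following to SAP 5.9.3:
- Summaries by actual dose level at the last administration before the sample. Day 1 samples are taken before dosing, so for C2D1, C9D1, C10D1 and C17D1 this is the previous cycle's dose.
- Dose-normalised post-dose concentrations, stated to assume approximate proportionality, with samples soon after a dose change flagged or excluded. As a guide, after a step from 0.8 to 1.0 mg/kg at steady state, the normalised pre-dose value is low by about 0.2 × 0.38 to 0.2 × 0.41, or 8%, after one dose at the new level. After two doses it is low by about 3% (0.2 × 0.38² to 0.2 × 0.41²).
- The dose given, as a column in the concentration listing.
- C1D1, C1D8 and C2D1 shown separately for patients with and without treatment interruption, leaving the C1D1 pre-dose values un-normalised.

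The dose data are already recorded and listed under SAP 5.5, so nothing new is collected. The cost is extra table columns and small numbers at some dose levels; the normalised summary offsets the latter because it does not divide patients into dose groups.
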